# 8.0 PRETREATMENT EVALUATION

The following tests must be completed prior to enrollment unless otherwise specified:

Prior to study entry (randomization):

patients approached (if applicable).

• Standard of care biopsy proving malignancy, with clinical documentation consistent with metastatic disease, per physician discretion.

Within 6 weeks (42 days) of study entry (randomization):

- CT CAP, FDG-PET/CT scan, MRI Total Spine or NaF-PET can be used, imaging study is at the discretion of the treating physician.
- Other local imaging studies that include the target lesion(s) can also be used as baseline imaging at the discretion of the treating physician.

Within 4 weeks (28 days) of study entry (randomization):

- CBC with differential
- Comprehensive metabolic panel (CMP=Na, K, Cl, CO2, BUN, Creatine, Ca, Glucose, total protein, albumin, alk phos, total bilirubin, AST and ALT).
- Complete medical history including current medications, comorbidities and performance status
- Physical exam including weight, height and vital signs (O2 saturation, blood pressure, heart rate, respiratory rate, and temperature).
- BPI short form and EQ-5D-5L
- Lesion Identification Worksheet should be completed by physicians

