## 10.0 EVALUATION DURING TREATMENT/INTERVENTION

All patients in Arm 2 (RT arm) will be assessed for toxicities according to CTCAE v 4.0 and pain score using BPI short form once every 5 treatment days. Only patients in Arm 2 (RT arm) will have radiation treatment related adverse event evaluation. Following randomization, all patients in Arm 1 and Arm 2 will be scheduled for follow-up at 3 months (+/- 4 weeks), 6 months (+/- 4 weeks), 12 months (+/- 4 weeks), and receive the following assessments:

- CBC with differential
- Imaging studies (Follow-up imaging at the discretion of the treating physicians)
- History and physical
- Performance status
- Adverse event evaluation (CTCAE V 4.0) (Excluding Arm 1 patients)
- BPI Short Form
- EQ-5D-5L

•

In the event of an SRE, the following assessments should be completed within one week. As it may not be feasible that the research team will be notified of all SREs within one week, or a patient may not be able to come to MSK, these assessments are optional, but highly recommended:

- CBC with differential
- Imaging studies (Follow-up imaging at the discretion of the treating physician)
- History and physical
- Performance status
- Adverse event evaluation (CTCAE v 4.0)
- BPI Short Form
- EQ-5D-5L

If patient is unable to come in for a follow-up appointment or within one week of an SRE occurring, a telephone follow-up will suffice. The CBC with differential, history and physical, performance status and imaging studies will be deferred. If the patient has had any of these assessments completed locally, records should be obtained to fulfill these requirements. If the attending physician is able, the adverse event evaluation can be completed over the phone.

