# 12.2 Secondary Outcome Measurements

Patients on both arms will be followed for accumulation of surrogates of health care cost, including number and duration of hospitalizations for SREs.

All study participants will be assessed for health related quality of life, measured using the BPI questionnaires, and health utilities using the EQ-5D-5L form.

Patients enrolled on both arms of the study will also be included in an analysis of pain-free survival, defined as time from study entry to start of opioids or death. Patients enrolled on both arms of the study will also be included in an analysis of overall survival, defined as time from study entry to death.

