## 14.0 BIOSTATISTICS

The primary objective of this study is to compare the rate of skeletal related events (SRE) from the date of randomization to death or 12 months, whichever occurs first, between patients who received standard of care versus upfront, early palliative RT to high-risk bone metastases. We expect 60-80% of the enrolled patients can be followed for 1 year. An SRE is defined as pathological fractures, spinal cord compression, or palliative radiotherapy and orthopedic surgery for bone pain. Data suggest that the event rate is around 60% in the standard of care arm . In our institutional experience, 75% of inpatient radiation consultation led to palliative radiation for painful bone

metastasis, an SRE. Furthermore, 61% of these lesions were diagnosed at least 4 months prior to undergoing RT. We believe 60% estimated event rate at 1-year is a conservative estimate.

The primary endpoint is a binary variable and the rate refers to proportion and is defined as the number of lesions that had SRE divided by the total number of target lesions. This analysis is lesion-based so an SRE (or no SRE) at one site does not affect the status of other sites from the same patient. We estimate that the investigational arm has the event rate around 30%. Radiation therapy is extremely effective in alleviating pain due to bone metastases with 70-80% pain control. By preventing the development of significant bone pain, which often leads to SREs, RT can effectively reduce SREs, To this end we will analyze at least 66 patients with valid SRE endpoint (randomized 1:1 to each arm) to achieve >80% power in detecting such a difference using a two-sample, one-sided proportion test with alpha<0.05. Since patients who withdraw before the endpoint can be evaluated will not be included in the analysis (i.e., it will NOT be an intent-to-treat analysis) we will over-accrue to account for withdrawals to ensure a minimum of 33 patients in each arm (subject to stratification, see Section 15.2) who can contribute the analyzable endpoint of SRE. We believe an additional 10% would be sufficient so totally we expect to randomize 74 patients. A small portion of patients (<15%) may have multiple lesions, in which case they will be treated as independent analysis units. In other words, the eventual effect sample size may be slightly higher than 66 because this objective will be analyzed per lesion.

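### A telephone contact can replace a visit with the history deferred, and no scheduled item asks about SREs, SRE admissions or opioid start, so ascertainment can be incomplete and can differ by arm

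*Combined protocol and SAP*

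**What the plan says.** Section 10.0 schedules both arms at 3, 6 and 12 months for blood count, discretionary imaging, history and physical, performance status, BPI and EQ-5D-5L. One further item is restricted by arm: "Adverse event evaluation (CTCAE V 4.0) (Excluding Arm 1 patients").

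If the patient cannot attend, a telephone contact is accepted instead, and "The CBC with differential, history and physical, performance status and imaging studies will be deferred". Three provisions follow:
- If any deferred assessment was done locally, its records are to be obtained.
- The adverse event evaluation may be done by phone if the attending physician is able.
- The two questionnaires may be completed by phone or sent by mail, fax or e-mail.

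A separate set of assessments is triggered by an SRE. It is optional, and the stated reason begins "As it may not be feasible that the research team will be notified of all SREs within one week".

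The endpoints that need these data are stated for both arms. Sections 12.1 and 14.0 make SREs primary, as a lesion-level proportion up to death or 12 months. Section 12.2 adds health-care cost surrogates, "including number and duration of hospitalizations for SREs", and pain-free survival, which ends at opioid start or death. Neither the Section 10.0 list nor its table has a row for any of these. The lesion worksheet is ticked only before randomization, and medication is spelled out only at baseline (Section 8.0): "Complete medical history including current medications, comorbidities and performance status".

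**The concern.** At an in-person visit a clinician taking a history would normally learn of a fracture, a course of palliative RT elsewhere, an admission or a new opioid. The telephone rule removes that step and puts nothing in its place. A remote contact can comply with the protocol without anyone asking about the primary endpoint.

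What remains also differs by arm. Both arms keep the BPI, which as described in Section 4.2.3 asks about current pain treatment but not when it began, and the EQ-5D-5L, which covers five health dimensions. Only Arm 2 keeps a scheduled adverse event evaluation. Section 11.0 lists rib and vertebral compression fractures among the RT toxicities, so that evaluation could bring to light events nobody asks about in Arm 1.

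At stake are the completeness and the between-arm comparability of the primary endpoint, and to a lesser degree of SRE hospitalizations and pain-free survival. The design has almost no power to spare.

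**Working it through.** **Step 1: what a contact run exactly as written can supply.**

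| Fact needed | In-person visit | Remote contact, Arm 1 | Remote contact, Arm 2 |
|---|---|---|---|
| SRE at a target lesion | History; imaging if done | Local records, if they exist and are known | Same, plus possible adverse event evaluation |
| SRE admission and dates | History | Local records, as above | Same, plus possible adverse event evaluation |
| Opioid use | History, BPI | BPI (current treatment) | BPI (current treatment) |
| Opioid start date | History | No listed item | No listed item |

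**Step 2: reproduce the planned size.** Inputs from Section 14.0:
- control rate: "Data suggest that the event rate is around 60% in the standard of care arm"
- RT arm: 30%
- test: "two-sample, one-sided proportion test with alpha<0.05"
- target: "to achieve >80% power in detecting such a difference"
- 33 evaluable patients per arm, and 10% over-accrual

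With pooled variance under the null and no continuity correction, where p̄ = (p1 + p2)/2:

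n per arm = [z0.95 √(2p̄(1−p̄)) + z0.80 √(p1(1−p1) + p2(1−p2))]² / (p1−p2)²

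= [1.645 √(2×0.45×0.55) + 0.842 √(0.24+0.21)]² / 0.30² = 32.9, so 33 per arm and 66 in all. Over-accrual: 66/0.90 = 73.3, so 74. Both match the plan.

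Power = Φ{[(p1−p2) − 1.645·SE0]/SE1}, with SE0 = √(2p̄(1−p̄)/n) and SE1 = √{[p1(1−p1) + p2(1−p2)]/n}.

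At n = 33: SE0 = 0.1225 and SE1 = 0.1168, so power = Φ(0.844) = 80.1%.

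**Step 3: illustrate under-ascertainment.** Two assumptions are needed, and the documents support neither with a figure or a rule: a fraction m of SREs is never learned of, and such a lesion is counted as having no event. Observed rates are then 0.60(1−m1) and 0.30(1−m2). If the Arm 2 evaluation recovers a share r of what would be missed, m2 = m1(1−r). There are 33 units per arm throughout.

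| m1 | Share recovered in Arm 2 (r) | Observed rates | Difference (points) | Power |
|---|---|---|---|---|
| 0 | – | 60% v 30% | 30 | 80.1% |
| 10% | 0 | 54% v 27% | 27 | 73.0% |
| 10% | 25% | 54% v 27.75% | 26.25 | 70.7% |
| 10% | 50% | 54% v 28.5% | 25.5 | 68.3% |
| 10% | 100% | 54% v 30% | 24 | 63.3% |
| 20% | 0 | 48% v 24% | 24 | 65.5% |
| 20% | 25% | 48% v 25.5% | 22.5 | 60.2% |
| 20% | 50% | 48% v 27% | 21 | 54.8% |
| 20% | 100% | 48% v 30% | 18 | 44.1% |

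Every row shrinks the observed difference. The direction would reverse only if Arm 2 lost more events than Arm 1 (10% missed in Arm 2 alone gives 60% v 27% and 86.9% power), and nothing in Section 10.0 points that way.

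**The case against.** The strongest reply is that the protocol leaves the content of the call unspecified, which is not the same as forbidding the question. Other routes exist:
- This is a single-institution trial with a coordinator assigned to data abstraction (Section 16.0).
- Section 4.1 intends the worksheet lesions to be followed in both arms.
- Section 12.2 commits both arms to follow-up for SRE hospitalizations.
- Section 11.2.1 names hospital notes as an adverse event source.
- Appendix 3 is titled as a tracking worksheet, though its content is not shown.

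This tempers the point without removing it. None of these routes is specified as SRE ascertainment at follow-up, and centre records need not show care given elsewhere.

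Four stronger readings are tempting, and the documents do not support them.
- *A remote Arm 1 contact always collects only two questionnaires.* The local-records provision contradicts this where such records exist, and the BPI partly shows opioid use.
- *An unasked lesion is counted as SRE-free.* No section says so. Section 14.0 confines the analysis to patients with a valid SRE endpoint and does not say how unknown status is coded.
- *Arm 2 ascertainment stays complete while Arm 1 loses events.* The phone evaluation depends on the physician being able to do it. Section 11.2.1 limits recording to non-hematologic events of grade 3 or higher. The evaluation is not a query for palliative RT or orthopedic surgery, and palliative RT is the SRE type behind much of the Section 14.0 rate rationale.
- *Extra BPI forms during RT bias pain-free survival.* That endpoint uses the start of opioids. Earlier detection would bias it only if the contact date were substituted, which no section says. Regimens of 1 to 10 fractions imply only about one or two such forms.

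**Conclusion.** The concern stands in a limited form. Two stated rules, deferral of the history at a telephone contact and restriction of the scheduled adverse event evaluation to Arm 2, combine with the lack of any endpoint item to allow SRE ascertainment that is incomplete and arm-dependent. The likely direction is dilution of an RT effect, so the main risk is lost power and a distorted estimate rather than a false positive.

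The size is unknown, because the documents give neither the share of remote contacts nor the share of SREs that would be missed. The power figures show only how thin the margin is. Within them, 63.3% and 44.1% are extreme bounds, because they require the Arm 2 evaluation to recover every missed event. An assumed recovery of 25% to 50% gives about 71% to 68% when 10% are missed, and 60% to 55% when 20% are missed. All of them rest on missed events being counted as no event.

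**What to change.** 1. In Section 10.0, take the history out of the items deferred at a telephone contact. The physical examination can stay deferred.
2. Add one row to the list and the schedule table at 3, 6 and 12 months, identical in both arms, completed in person or remotely and never deferrable. For each worksheet lesion, ask about any fracture, cord compression, RT or orthopedic surgery since the last contact, with date and place, including outside hospitals. Ask also for any SRE-related admission with its dates, and the date of first opioid use.
3. State that the analyses use event dates, not contact dates.
4. Reconcile Section 13.0, under which participation ends when an SRE occurs, with Section 14.0, under which each lesion is assessed to death or 12 months whatever happens at other sites. Without this, the new row could not be completed for a patient's remaining lesions after a first SRE.
5. Reconcile the Arm 1 exclusion from adverse event evaluation in the Section 10.0 list with the schedule table, whose row carries no arm restriction.

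The cost is a short case report form, a few more minutes per contact and a protocol amendment. No new visit or procedure is needed.

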# 6.1 Subject Inclusion Criteria

- Histologically confirmed solid tumor malignancy with greater than 5 sites of metastatic disease detected on imaging.
- Has high risk bone metastases that are asymptomatic or minimally symptomatic (not requiring opioids). High risks metastases are defined as: 1. bulkiest sites of osseous disease ≥ 2cm, 2. disease involving the hip (acetabulum, femoral head, femoral neck),

Page **12** of **30** Version: 2/26/16

shoulder (acromion, glenoid, humeral head), or sacroiliac joints 3. disease in long bones with1/3-2/3 cortical thickness (humerus, radius, ulna, clavicle, femur, tibia, fibula, metacarpus, phalanges) 4. disease in junctional spine (C7-T1, T12-L1, L5-S1) and/or disease with posterior element involvement.

- ECOG performance status 0 − 2.
- Age ≥ 18 years.
- Able to provide informed consent.
- Patients at reproductive potential must agree to practice an effective contraceptive method. Women of childbearing potential must not be pregnant or lactating.

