#### 9.0 TREATMENT/INTERVENTION PLAN

Patients who have metastatic cancer and greater than 5 sites of disease will be enrolled. Patients may also have newly diagnosed stage IV disease. Patient will be randomized to standard of care therapy or to receive RT to selective bone metastases prior to continuation of standard therapy.

9.1 RT

Page **14** of **30** Version: 2/26/16

Patients will undergo RT to each lesion using one of the dose and fractionation regimens in the table below. Accounting for the patient"s global clinical status, the treating radiation oncologist should select a RT regimen that would result in optimal lesion local control while not exceeding local normal tissue radiation tolerance:

Page **15** of **30** Version: 2/26/16

Total Dose	Fractions	Dose per Fraction	Verification Imaging
2000cGy	5	400cGy	MV or KV
3000cGy	10	300cGy	MV or KV
3000cGy	5	600cGy	KV and CBCT
3500cGy	5	700cGy	KV and CBCT
2400cGY	3	800cGy	KV and CBCT
2700cGy	3	900cGy	KV and CBCT
2400cGy	1	2400cGy	KV and CBCT

Patients will first be simulated using appropriate immobilization as determined by the treating radiation oncologist. This will be followed by acquisition of a CT scan in the treatment position. The use of intravenous or oral contrast will be at the discretion of the treating radiation oncologist. Dose constraints will be followed according to department standards and will depend on the radiation technique and total dose prescribed.

The treating radiation oncologist must delineate the gross tumor volume (GTV). Clinical target volume (CTV) will be defined as the GTV plus a margin required for microscopic extension of tumor. The planning target volume (PTV) should expand the CTV by an amount necessary to account for uncertainty in patient positioning and treatment delivery.

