Additionally, the BPI Short Form and EQ-5D-5L can be completed over the phone or sent to the patient via mail, fax or electronic mail by the physician, physician office assistant or research staff. For SRE, it is preferred that the BPI Short Form and EQ-5D-5L are completed over the phone if patients are unable to come in for a follow-up appointment. If the patient cannot be reached by phone or prefers to complete the questionnaires personally, the questionnaires will be sent via mail, fax or electronic mail. The questionnaires sent directly to patients must be blank forms with no patient identifiers, only study ID numbers. If questionnaires are sent via mail, the patient must be provided with a pre-filled business envelope that will allow patients to return it with no expense. Patients must also have the option of returning questionnaires by electronic mail or fax. If a patient is unable to come in for a follow-up appointment or complete the questionnaires over the phone, the method by which questionnaires are sent to patients and the method by which questionnaires are returned will be determined based on the patient's preference or if they are unable to be contacted by phone, the contact information on file for the patient as some patients may not have access to a phone, fax or electronic mail.

Page **17** of **30** Version: 2/26/16

	Prior to randomizati on	Within 4 weeks prior to randomiz ation	Once every 5 treatment days during radiation	3 months following randomizat ion +/- 4 weeks	6 months following randomizat ion +/- 4 weeks	12 months following randomizat ion +/- 4 weeks	Within one week of SRE 
Standard of care biopsy of a metastatic lesion or pathology review confirming metastatic cancer 	Х						
CBC with differential		X		X	X	X	X
CMP		Х					
lmaging studies 		Х		X 	X 	X 	X 
History and physical		X		X 	X 	X 	X 
Performance status		Х		X	X	Х	Х
Adverse event evaluation (CTCAE v 4.0)			X	X	X	X	Х
BPI Short Form		Х	Х	Х	Х	Х	X
EQ-5D-5L		Х		X	X	X	X
Lesions Identification Worksheet		Х					

<sup>1 For patients with prostate cancer, an elevated PSA consistent with metastatic disease is adequate in the absence of a biopsy.

<sup>2 Follow up imaging at the discretion of the treating physician. The same imaging modality is encouraged for assessment between time points.

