#### 13.0 CRITERIA FOR REMOVAL FROM STUDY

Patients will be removed from the study if any of the following criteria are met, after review by the principal investigator:

- 1. A change in the patient's medical status unrelated to RT results in the patient being unable to comply with the protocol.
- 2. Patient is unable to continue follow-up as outlined within the protocol
- 3. Patient is found to be ineligible based on the criteria in section 6.0 of this protocol.
- 4. Patient requests to withdraw from the protocol.
- 5. Patient death.

Otherwise, patients will continue on protocol until 12 months have elapsed since date of randomization or until an SRE occurs.

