# 15.0 RESEARCH PARTICIPANT REGISTRATION AND RANDOMIZATION PROCEDURES

## 15.1 Research Participant Registration

Confirm eligibility as defined in the section entitled Inclusion/Exclusion Criteria. Obtain informed consent, by following procedures defined in section entitled Informed Consent Procedures. During the registration process registering individuals will be required to complete a protocol specific Eligibility Checklist. The individual signing the Eligibility Checklist is confirming whether or not the participant is eligible to enroll in the study. Study staff is responsible for ensuring that all institutional requirements necessary to enroll a participant to the study have been completed. See related Clinical Research Policy and Procedure #401 (Protocol Participant Registration).

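### Section 13 item 3 allows randomised patients found ineligible to be removed with the arm already known, in a trial whose primary analysis is not intent-to-treat; schedule footnote 1 is one way this can arise

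*Combined protocol and SAP*

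**What the plan says.** **Removal.** Section 13 opens: "Patients will be removed from the study if any of the following criteria are met, after review by the principal investigator". Item 3 of its list is: "Patient is found to be ineligible based on the criteria in section 6.0 of this protocol". Patients to whom no item applies stay on protocol until 12 months after randomisation or an SRE. Removal therefore appears to end follow-up, although the section does not say so outright.

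**Analysis.** Section 14 leaves out of the primary analysis patients who withdraw before their endpoint can be assessed, and states that the analysis is not intent-to-treat. It requires 66 patients with a valid SRE endpoint (33 per arm) and randomises 74. It does not mention patients removed as ineligible.

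**Proof of cancer.**
- Section 6.1: "Histologically confirmed solid tumor malignancy with greater than 5 sites of metastatic disease detected on imaging"
- Section 8.0: "Standard of care biopsy proving malignancy, with clinical documentation consistent with metastatic disease, per physician discretion"
- Section 10.0, schedule table row: "Standard of care biopsy of a metastatic lesion or pathology review confirming metastatic cancer"
- Section 10.0, footnote 1 to that row: "For patients with prostate cancer, an elevated PSA consistent with metastatic disease is adequate in the absence of a biopsy"

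**Order of events.** Section 15.1 instructs staff as follows: "Confirm eligibility as defined in the section entitled Inclusion/Exclusion Criteria". Under Section 15.2 randomisation comes only after eligibility is established, and physicians learn the arm within 24 hours of it. Section 16.2 has the principal investigator verify each case at enrolment.

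**The concern.** Item 3 creates an exclusion that takes effect after randomisation and rests on a judgement made when the arm is known. No blinding of the review is described, and no criterion for the decision is given beyond failure of Section 6.0. If a removed patient leaves follow-up and supplies no endpoint, the patients compared are no longer those who were randomised. A few such exclusions could shift the comparison if the decision to look again at a patient's eligibility is related to arm or prognosis.

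For item 3 to matter, a patient must be randomised and later judged to fail Section 6.0. The differing statements on proof of cancer offer one way. A coordinator working from the schedule table could accept a prostate cancer patient on PSA alone. A later check against Section 6.1, for instance one of the compliance audits that Section 16.1 requires at least twice a year, could then find that patient ineligible.

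**Working it through.** **1. Passages side by side.** Take a prostate cancer patient with an elevated PSA and no biopsy of any kind.

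| Place | Would this patient pass? |
|---|---|
| Section 6.1 | No: histological confirmation, no exception |
| Section 8.0 | No: a biopsy proving malignancy is required |
| Schedule row alone | No: biopsy of a metastasis, or pathology review |
| Footnote 1 read broadly | Yes |
| Footnote 1 read as waiving proof of metastasis only | No: the primary must still be confirmed |
| Section 13 item 3 | Refers only to Section 6.0, so the patient can be removed |

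The conflict with Section 6.1 exists only on the broad reading. A smaller mismatch remains on either reading. A patient with a biopsied primary and metastases documented clinically satisfies Sections 6.1 and 8.0 but arguably not the schedule row. That patient could not be removed under item 3.

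**2. What happens to a removed patient.** Section 13 ends protocol follow-up by implication. Section 14 counts patients with a valid SRE endpoint. A patient removed before the endpoint would not contribute unless follow-up continued. This is an inference, because Section 14 does not address the case.

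**3. The plan's own figures.** Inputs from Section 14: event rates 0.60 and 0.30, one-sided alpha 0.05, power above 80%, 1:1 allocation.

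n per arm = [z(0.95)·√(2·p̄·(1−p̄)) + z(0.80)·√(p1(1−p1) + p2(1−p2))]² / (p1−p2)², with p̄ = 0.45

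= [1.645·√0.495 + 0.842·√0.45]² / 0.30² ≈ 32.9, so 33 per arm, or 66.

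Power at 33 per arm = Φ[(0.30·√33 − 1.645·√0.495)/√0.45] ≈ Φ(0.844) = 0.8006.

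With a 10% allowance, 66/0.90 = 73.3, so 74. The plan's numbers reproduce.

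**4. Size of a loss.** The reserve is 74 − 66 = 8. Assume that ordinary withdrawals use all of it, and that removals fall equally on the arms. Power by the same formula:

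| Removed as ineligible | Evaluable | Power |
|---|---|---|
| 0 | 66 | 0.8006 |
| 1 | 65 | 0.7951 |
| 2 | 64 | 0.7895 |
| 4 | 62 | 0.7778 |
| 8 | 58 | 0.7528 |

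If there were no other withdrawals, up to 8 removals would be absorbed (74 − 8 = 66). The documents give no count of prostate cancer patients or of patients without histology, so 0 to 8 is an assumed range.

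**5. Size of a selective loss (illustration).** Count one lesion per patient. Expected events are 0.60·33 = 19.8 and 0.30·33 = 9.9. Suppose one patient is removed from the RT arm who would have gone on to an SRE, and one from standard of care who would not. The proportions become 19.8/32 = 61.9% and 8.9/32 = 27.8%. The difference moves from 30 to about 34 percentage points. This is the least favourable pattern, and nothing in the documents shows that it would occur.

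**The case against.** The strongest reply is that Section 6 already governs. Section 15.1 sends staff to the inclusion and exclusion criteria with a signed checklist, Section 15.2 allows randomisation only after eligibility is established, and Section 16.2 adds verification by the principal investigator. A PSA-only patient would have to pass all three. Footnote 1 also has a reading that fits Section 6.1: it hangs on a row about proving metastasis and speaks of PSA consistent with metastatic disease, so it may waive only that proof in a patient whose primary is already confirmed. The eligibility wording is the same for both arms, and the power loss is small.

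Most of this stands, and it makes the route narrow. It does not remove item 3, which is written for ineligibility found after those checks, from whatever cause. Principal investigator review does not guard against selection when the arm is known.

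Several stronger readings are tempting but unsupported:
- **That no passage says which text governs.** Section 15.1 does.
- **That the site threshold differs.** Sections 6.1 and 9.0 both say greater than 5, and the schedule table gives no threshold. Section 9.0 ("Patients who have metastatic cancer and greater than 5 sites of disease will be enrolled") only omits the qualifier, in a sentence that already requires metastatic cancer. It would matter only if a primary tumour were counted as a site.
- **That a PSA-only patient could not be stratified by histology.** Section 15.2 does not define the histology categories, and nothing prevents assignment to a prostate stratum.
- **That some percentage of the 74 would be lost.** The documents give no basis for a figure.

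**Conclusion.** The point holds in a limited form. As written, the plan permits a discretionary exclusion after randomisation, made with the arm known, and does not say how the excluded patients are analysed. The differing statements on proof of cancer are one route to it, and only if footnote 1 is read broadly and the checks before randomisation miss the case. The number affected is unknown and may be zero.

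The effect on power is modest: from 0.8006 to 0.7778 for four removals, assuming the reserve of 8 is already spent and removals are balanced. Possible selection matters more than lost power, but the documents show no mechanism that would make removal differ by arm. A reader might infer that the randomised comparison is already broken or that the trial is too small. Neither follows, and the stated sample size and power are not wrong on this point. The change is worth making because it is cheap and closes the gap whatever the cause of late-found ineligibility.

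**What to change.** 1. **Section 13 item 3.** Provide that a randomised patient later found ineligible is recorded as a protocol deviation and stays in follow-up for SRE and survival. This concerns follow-up and analysis only, not treatment.
2. **Section 14.** Add a sentence that such patients are analysed in the arm to which they were assigned.
3. **Sections 6.1 and 8.0, the schedule row and footnote 1.** Reconcile them so that they state one requirement for proof of malignancy and one for proof of metastasis, and say whether the footnote waives both or only the second. The sponsor should choose the wording.
4. **Section 9.0 (minor).** Repeat the qualifier from Section 6.1, so that the count is of metastatic sites.

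The cost is amendment text in these sections, with no change to the sample size. The downside is small: a few ineligible patients may remain in the analysed set.
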